For the primary analysis (and related secondary analyses), we make the following assumptions:

- Death is reported without error.
- Other components of the primary endpoint may be subject to under-reporting and misclassification but these errors are non-differential, i.e. probability of an error is consistent across randomized treatment groups.
- Patient self-report with confirmation is assumed to have nearly perfect specificity since incorrect self-reports will be excluded by examination of medical record. There may be some under-reporting since identification of the event depends on self-report. Some selfreported events may not be confirmed or contradicted if participant did not consent to confirmation process.
- CDM endpoints may be under-reported since participants may be treated for events outside the CDM health systems or events within the health system may be missed. Misclassification may occur due to imperfect electronic phenotype definitions.
- Claims data (CMS and private) is assumed to be complete for enrolled participants and changes in enrollment status are independent of trial outcome. Misclassification may occur due to imperfect electronic phenotype definitions.

We will perform two sets of sensitivity analyses: 1) to assess impact of under-reporting on the primary analysis and 2) to assess impact of misclassification on the primary analysis. Because available data sources vary across participants, we summarize the potential for error due to under-reporting and misclassification according to each potential combination of available data. To simplify classification of participants, we will not attempt to account for changes in data sources over time, but rather classify participants according to data sources available for more than half of follow-up time.

	Data sources available			Potential error		
Scenario	Self- report	Out of Network Confirmation	CDM	Claims (CMS or private)	Under- reporting	Misclassification
1	Х				Yes	Yes
2	Х	Х			Yes	No
3	х		Х		Yes	Yes
4	Х			Х	No	Yes
5	Х		Х	Х	No	Yes
6			Х		Yes	Yes
7				Х	No	Yes

8		Х	Х	No	Yes
9*				Yes	No

*Only information is vital status check at end of trial.

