To assess impact of under-reporting due to participants moving or seeking care outside of the CDM health system, we will repeat the primary analysis modifying the censoring rules for CDM data such that the censoring date will be the last date the patient encountered the health system. This will include inpatient and outpatient visits, labs, vitals and prescription medication fills. All other censoring dates will remain the same.

Under the assumption that under-reporting is non-differential between treatment groups, the impact on primary analysis inference would be a loss of power. If the primary result is non-significant then we will assess overall impact of under-reporting, by performing a tipping point analysis to identify how many events would have to be missed to achieve significance. We will take an approach that is adapted and simplified from that described by Little et al (2016) for a sensitivity analysis for missing data. A Weibull model of the primary endpoint will be fit to the entire ITT population, with independent variables including an indicator that participant is at risk for under-reporting (Scenarios 1, 2, 3 and 6 in the table) and selected baseline characteristics. Other independent variables may be considered. Events will be sequentially added for those participants at risk of under-reporting across treatment groups. For each increment, *i* events will be imputed from the Weibull model 1000 times. A Cox model as specified for the primary analysis will be fit to the resulting dataset and treatment effect hazard ratio will be estimated, with standard errors adjusted using standard multiple imputation combining rules. The increment will be increased until the upper limit of the 95% CI for the HR of the treatment effect crosses 1.0.

To assess impact of misclassification of electronic phenotype definitions, we will repeat the primary analysis modifying the code-based definitions of primary endpoints to include codes in 1) principal position only and 2) any position.

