To further assess impact of misclassification, we will perform a tipping point analysis expanding on methods developed by Liublinska and Rubin (2014) for missing data in clinical trials. Positive predictive value and negative predictive value will be varied from 0 to 1 to reclassify events or non-events for those participants at risk of misclassification (Scenarios 1 and 3-8). For each combination of PPV and NPV, the corresponding number of reclassified events will be imputed 1000 times. Reclassified events will randomly selected and set to non-events. Reclassified non-events will be generated from the Weibull model described in tipping analysis for under-reporting. A Cox model as specified for the primary analysis will be fit to the resulting dataset and treatment effect hazard ratio will be estimated, with standard errors adjusted using standard multiple imputation combining rules. A 95% confidence interval will be calculated for the HR of the treatment effect. Resulting inference based on comparing confidence limits to 1.0 will be presented in a heat map with positive predictive value and negative predictive value reported on the x- and y-axes. Note that this analysis does not relax the assumption of consistency of misclassification across treatment groups.

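### The under-reporting tipping-point analysis in SAP 7.10 leaves scenario 9 out of its at-risk set and stops only on the upper confidence limit

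*SAP*

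**What the plan says.** SAP 7.10 classifies participants by the data sources available to them and marks, for each of nine scenarios, whether under-reporting and misclassification are possible. Scenario 9 has no self-report, CDM or claims source. Its footnote reads "Only information is vital status check at end of trial", and its under-reporting column says Yes. Among the assumptions for the primary analysis is "Death is reported without error".

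The under-reporting analysis runs only if the primary result is non-significant. Its premise is that, if under-reporting is non-differential, "the impact on primary analysis inference would be a loss of power". Its aim is "to identify how many events would have to be missed to achieve significance". A Weibull model is fitted with covariates that include "an indicator that participant is at risk for under-reporting (Scenarios 1, 2, 3 and 6 in the table) and selected baseline characteristics", and the SAP adds "Other independent variables may be considered". Events are then imputed for at-risk participants in growing increments, 1,000 times each. The Cox model is refitted and the results are pooled by multiple-imputation rules. The stopping rule is "The increment will be increased until the upper limit of the 95% CI for the HR of the treatment effect crosses 1.0".

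SAP 7.3 makes the primary test two-tailed at 0.05. Neither document names the reference arm for the hazard ratio.

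**The concern.** This is the SAP's planned check on whether missed events could explain a null result, so its rules should follow the SAP's own table and its own two-tailed test. On two counts they do not.

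The participants with the least information on MI and stroke are treated as if none of their events could be missing. The search also tests for significance in one direction only, while the documents leave the direction open. The Bayesian paragraph of SAP 7.10 calls prior information on direction neutral, protocol II.C.4 allows that higher doses may prove better, and SAP 7.6 speaks of a higher risk arm without naming a dose. If the estimate falls above 1, the search could pass a real tipping point and carry on with no end defined.

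**Working it through.** **1. Scenario lists side by side (SAP 7.10).**

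| Error | Marked Yes in the table | Used in the analysis |
|---|---|---|
| Under-reporting | 1, 2, 3, 6, 9 | 1, 2, 3, 6 |
| Misclassification | 1, 3 to 8 | 1, 3 to 8 |

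The second row matches exactly; the first drops scenario 9 without a reason. The assumption on deaths does not explain the omission, because a vital-status check cannot show a nonfatal MI or stroke. No scenario sizes are given, so no number can be attached. SAP 7.5 does not list the vital-status check among its sources of follow-up time, so part of this time may already be censored.

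**2. The stopping rule when the HR is above 1.** The plan gives no figure to reproduce, so this is an illustration. Inputs: D = 1,322 events (SAP 7.6), an assumed observed HR of 1.111 (1/0.90, log 0.1054), arm in the imputation model, parameters held fixed, and m = 1,000 imputations.

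The share of events in the numerator arm is p = 1.111/2.111 = 0.5263, so 1/[p(1 − p)] = 4.011. After i added events, with X ~ Bin(i, p) of them in that arm, the delta method gives:

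- within-imputation variance W = 4.011/(D + i)
- between-imputation variance B = W × i/(D + i)
- total variance T = W + (1 + 1/m)B

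Results:

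- i = 0: T = 0.003034, SE 0.0551, z = 1.91, not significant.
- i = 370: W = 4.011/1,692 = 0.002371, T = 0.002371 × 1.219 = 0.002890, SE 0.0538, z = 1.96. The lower limit reaches 1.0; the upper limit is about 1.23.
- i = 5,000: W = 4.011/6,322 = 0.000634, T = 0.000634 × 1.792 = 0.001137, SE 0.0337. The interval is about 1.04 to 1.19.

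Significance is reached near 370, but the upper limit never approaches 1.0, so the written rule does not stop.

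The count of 370 is rough. A participant-level simulation used 15,000 participants, half assumed at risk, observed HR 0.901 and 1,251 events, with arm in the model and fixed parameters. It gave z of −1.85, −1.85, −1.92 and −1.99 at 0, 370, 1,000 and 2,000 added events. It tipped between 1,000 and 2,000, where the event-count formula gives about 620. A separate Cox simulation with observed HR 1.097 (1,318 events, 40 imputations, a simpler exposure-weighted draw) had limits of 1.018 and 1.199 at 2,000 added events, the same pattern.

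**3. Secondary: arm in the Weibull model.** Take an assumed HR of 0.90, so D1 = 1,322 × 0.90/1.90 = 626.2 and D0 = 695.8; at the start z = −1.91.

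- *Arm left out.* Added events split about equally. At i = 1,000, log HR = ln(1,126.2/1,195.8) = −0.0600, W = 0.001724, B = 250 × W² = 0.000743, T = 0.002468 and z = −1.21. In the participant-level simulation z went from −1.85 to −1.04 at 1,000.
- *Arm in, parameters drawn.* Let V0 = 4.011/D. Then W = V0·D/(D + i). B is the binomial part V0·D·i/(D + i)² plus the parameter part V0·i²/(D + i)², which sum to V0·i/(D + i). So W + B = V0 for every i, and z stays at about −1.91 (ignoring the 1/m term). Simulated values stayed between −1.90 and −1.93 through 10,000 added events.
- *Arm in, parameters fixed.* z can reach 1.96 in absolute value, as in step 2, but this understates uncertainty.

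**The case against.** The strongest defence of the stopping rule is that protocol Table 6 and SAP 7.6 express effects as a reduction relative to the higher risk arm, with every relative risk below 1. On that convention the upper limit is the right one to watch. An analyst who saw the lower limit pass 1.0 would also know that the stated aim had been met. Coding the arms so that the HR is below 1 would indeed solve the problem. But those are power assumptions that do not define the reported HR, and the coding is not written down. The misclassification analysis in the same section compares confidence limits in the plural.

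On scenario 9, it is fair that the group may be small, partly censored already, or overlap with participants who withdrew. The withdrawal tipping-point analysis in SAP 7.9.2 does not clearly cover it, because it concerns withdrawn consent and runs only above 5%.

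A reader might also infer that the SAP excludes randomized arm from the imputation model. It does not: the covariate list is open, so this is a choice left unmade. Nor should a reader infer that adding arm makes the search work. With drawn parameters, the usual companion of the pooling rules the SAP cites, z does not move at all.

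**Conclusion.** Two rules are wrong as written: the at-risk set contradicts the SAP's own table, and the stopping rule is one-sided for a two-tailed question. The first has unknown size. The second bites only if the reported HR is above 1. The illustration assumes an HR of 1.111, 1,322 events, arm in the model and fixed parameters, and its count of 370 is probably too low.

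The handling of arm is a secondary note, not an error. Leaving arm out pulls the HR toward 1, contrary to the premise that non-differential under-reporting costs only power.

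Severity is minor. A reader might infer that the trial's main conclusion is at risk, but the documents do not support that. The analysis is conditional on a null result and supportive, and the primary estimate and test are unaffected.

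**What to change.** In SAP 7.10:

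1. Define the at-risk set as scenarios 1, 2, 3, 6 and 9. For scenario 9, add MI and stroke only, since death is assumed fully reported.
2. Name the reference arm for the HR. Stop when the 95% interval excludes 1.0 on the side of the observed HR, or when the event-free at-risk participants are used up. In the second case, report that no tipping point was found.
3. Include randomized arm in the Weibull model, and state in advance whether its parameters are drawn or fixed, with the consequence of each. This step alone does not guarantee an informative search.

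The cost is a few sentences and slightly more analysis work, with no new data. The downside is that the search may often end with no tipping point found.

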This endpoint includes death from any cause (all-cause mortality).

III.E.4.b. Hospitalization for Nonfatal MI

The endpoint of hospitalization for nonfatal MI will be ascertained using ICD-10-CM diagnosis codes (to be listed in the SAP) associated with an encounter in a hospital setting. Priority will be given to diagnosis codes in the principal or primary position. Diagnosis codes in secondary or unknown positions also will be searched for the identification of potential endpoints. The extent to which events identified by diagnosis codes in secondary or unknown positions will or will not be used in the final analysis will be detailed in the SAP. The MI coding algorithm that will guide these efforts was validated for use in FDA's Mini-Sentinel program⁹² and has been shown to have a positive predictive value (PPV) of 86%. 93

III.E.4.c Hospitalization for Stroke

The endpoints of hospitalization for hemorrhagic stroke or ischemic stroke will be ascertained using ICD-10-CM diagnosis codes (to be listed in the SAP) associated with an encounter in a hospital setting. Priority will be given to diagnosis codes in the principal or primary position. Diagnosis codes in secondary or unknown positions also will be searched for the identification of potential endpoints. The extent to which events identified by diagnosis codes in secondary or unknown positions will or will not be used in the final analysis will be detailed in the SAP. The stroke coding algorithm that will guide these efforts has been shown to have a PPV 85% or greater. Is chemic stroke hospitalizations and hemorrhagic stroke hospitalizations will be incorporated into a combined endpoint of all stroke events.

III.E.4.d. Coronary Revascularization

Coronary revascularization includes all coronary revascularization procedures (PCI/CABG) performed during the study. These will be identified using ICD-10-PCS procedure codes and CPT procedure codes (to be listed in the SAP).

III.E.4.e. Hospitalization for Major Bleeding

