5.3 Primary Safety Endpoint

The primary safety endpoint is hospitalization for major bleeding. Bleeding events include intracranial hemorrhage, GI bleeding, bleeding in other locations, or a control of bleeding procedure. To qualify as a major bleeding event, there also must be documented evidence of a blood product transfusion within +/- 7 days of the bleed.

6 Identification of Endpoints

The method for identification of clinical endpoints is documented in the protocol. Endpoints were identified through electronic sources (including EHR [PCORnet CDM], CMS claims or private insurance claims data) or patient reported via the patient portal (see figure below). Confirmation by electronic data is required for patient reported clinical endpoints. Some clinical endpoints, based on patient-reported events that could not be confirmed or refuted by the data sources listed above, were confirmed through medical record review.

For endpoints based on a hospitalization for a specific reason (MI, stroke, bleeding), the primary analysis will include endpoints identified by diagnostic codes both (a) in the principal position, and (b) for which the position is unknown. In the CMS and private insurance claims data, diagnostic code position for inpatient encounters is usually known, and we will use all codes reported. In the PCORnet EHR data, most, but not all, sites consistently use the principal/secondary designation for diagnoses. When diagnosis position is unavailable for a specific code, its position is recorded as "Other/Unknown" in the PCORnet CDM. Therefore, in the PCORnet data, when diagnosis position is available, only codes in the principal position will be used; but when diagnosis position is unavailable, all codes will be used. This requirement will ensure that we do not exclude events from sites that do not record this information. We will use diagnosis codes known to be (and designated as) secondary in sensitivity analyses only. More details on endpoint extraction are contained in the Query Technical Specifications.

Sensitivity analyses, including analyses addressing potential misclassification in endpoint definitions, are described in Section 7.10.

7 Summary of Statistical Methods

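### The misclassification tipping-point rule in SAP 7.10 does not exempt deaths, which the same section treats as error-free, so its PPV axis is not the PPV of the coding algorithms

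*SAP*

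**What the plan says.** Section 7.10 of the SAP lists the assumptions behind the primary and related secondary analyses. The first is "Death is reported without error". The next allows under-reporting and misclassification only in the other components, equally in both arms. For CDM and claims data, misclassification is put down to imperfect electronic phenotype definitions. In the scenario table, Scenario 9 (vital status check only) is marked as having no misclassification.

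The heat-map analysis later in the section reads differently:

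- **Grid:** "Positive predictive value and negative predictive value will be varied from 0 to 1 to reclassify events or non-events".
- **Who is eligible:** "for those participants at risk of misclassification (Scenarios 1 and 3-8"). Selection is by a participant's data sources, not by type of event.
- **Removed events:** "Reclassified events will randomly selected and set to non-events".
- **Added events:** generated from the Weibull model of the under-reporting analysis, which is fitted to the primary endpoint as a whole.
- **Refit:** "A Cox model as specified for the primary analysis will be fit to the resulting dataset", so the endpoint is still the composite that includes all-cause death.

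The only assumption that the SAP names as not relaxed here is equal misclassification across arms. Deaths are not mentioned.

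In the protocol, Section III.E.4.b says that the MI algorithm "has been shown to have a positive predictive value (PPV) of 86" percent. Section III.E.4.c gives 85% or greater for stroke.

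**The concern.** A programmer who follows the text would draw from all primary-endpoint events of participants in Scenarios 1 and 3-8 and turn some deaths into event-free follow-up. The section gives no ground for that. Its stated target is code-based phenotypes, and under the protocol deaths come largely from other sources (discharge disposition, Medicare death data, call-center vital status checks and site notification). A death in Scenario 5 could be erased while one in Scenario 9 could not. That is not the pattern expected if the death assumption were being relaxed on purpose.

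Two consequences follow. First, the PPV axis becomes a composite PPV, so the cited MI and stroke values do not lie on it. Second, if deaths are error-free, every cell with PPV below the death share of first events is impossible, yet those cells would be shown. The same gap affects the NPV side: under the stated assumption missed events can only be nonfatal MI or stroke, but they are drawn from a composite model.

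The trial has no events committee, and SAP Section 5.1 keeps the validation results out of the primary analyses. This is the only planned tipping-point analysis of misclassification, so readers will take its boundary at face value.

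**Working it through.** **Inputs.** D = 1322 primary events and a 15% relative risk reduction, taken as HR 0.85 (SAP Section 7.6); 1:1 allocation; two-sided 0.05; MI PPV 0.86 (protocol III.E.4.b). Assumed, because the documents do not give them: the death share d of first events, the component hazard ratios, all participants in Scenarios 1 and 3-8, and NPV 1.

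**Plan's own figure.** The heat map has no stated figure. The nearest is 88% power with 1322 events. The Schoenfeld formula gives z0 = |ln 0.85| × √1322 / 2 = 0.1625 × 18.18 = 2.95, hence power Φ(2.95 − 1.96) = 84%. The 88% is not reproduced, but that mismatch does not bear on this point.

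**Events removed at PPV 0.86.** 0.14 × 1322 = 185. With d = 0.40 to 0.70, deaths make up 0.40 × 185 = 74 to 0.70 × 185 = 130 of them. Only 111 to 56 could be coding errors.

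**What a component PPV means on the composite scale.** If deaths are error-free, composite PPV = d + (1 − d) × component PPV, which cannot fall below d. A component PPV of 0.86 becomes 0.40 + 0.60 × 0.86 = 0.92 at d = 0.40, 0.93 at d = 0.50 and 0.96 at d = 0.70.

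**Test statistic at PPV P, with multiple-imputation variance.**

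- Literal rule: total variance = 4/(DP) + 4(1 − P)/(DP) = 4(2 − P)/(DP). At P = 0.86 this is 4 × 1.14 / (1322 × 0.86) = 0.00401, so z = 0.1625 / 0.0633 = 2.57.
- Deaths fixed, same HR in every component: Dn = D[d + (1 − d)P], and total variance = 4/Dn + 4P(1 − P)(1 − d)D/Dn². At d = 0.50, P = 0.86: Dn = 1229, variance = 0.00325 + 0.00021 = 0.00346, so z = 0.1625 / 0.0589 = 2.76.

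**Where significance is lost.** For the literal rule, set k = (1.96/2.95)² = 0.44; then P = 2k/(1 + k) = 0.88/1.44 = 0.61. For deaths fixed, the variance above was solved numerically. As P goes to 0, z goes to z0√d, which stays above 1.96 once d exceeds about 0.44.

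| Death share | Literal rule | Deaths fixed, HR 0.85 throughout | Deaths fixed, death HR 1.0 | Deaths fixed, death HR 0.75 |
|---|---|---|---|---|
| 30% | 0.61 | 0.38 | 0.63 | never |
| 40% | 0.61 | 0.20 | 0.63 | never |
| 50% | 0.61 | never | 0.64 | never |

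The last two columns keep the overall HR at 0.85 by adjusting the nonfatal HR.

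**The case against.** The strongest reply is that the SAP never says deaths are reclassified. Read as a whole, the section concerns coded hospitalizations, and a careful programmer would exempt deaths. SAP Section 6 also points to Query Technical Specifications for endpoint extraction, which were not available here. The listed assumptions are stated for the primary and related secondary analyses, and the section says that its sensitivity analyses test violations of them. This stands to the extent that a reader who infers an outright contradiction goes too far: the inclusion of deaths follows from silence. It does not remove the problem, because the operative sentences select by participant, act on events without qualification and refit the composite.

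A second reply is that the difference is only one of axis. With equal hazard ratios and 50% deaths, the literal rule at composite PPV 0.93 gives z = 2.75, against 2.76 with deaths fixed at component PPV 0.86. That is correct, but it depends on equal hazard ratios. With a death HR of 1.0 and 50% deaths, the deaths-fixed boundary of 0.64 is 0.50 + 0.50 × 0.64 = 0.82 on the composite scale, while the literal map puts it at 0.61. No single relabelling repairs the map.

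A reader might also infer the following, which the documents do not support:

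- **The heat map is the main evidence on coded endpoints.** The SAP also repeats the primary analysis with principal-position codes only and with codes in any position, and it reports a separate validation.
- **The grid is too coarse or too wide.** "Positive predictive value and negative predictive value will be varied from 0 to 1" gives no step size, and showing the full range is a legitimate choice.
- **Scenario 1 can hold only deaths and should be dropped.** It rests on self-report alone, and SAP Section 6 says "Confirmation by electronic data is required for patient reported clinical endpoints". But participants are sorted by the sources held for more than half of follow-up, so coded events from the remaining time are possible.
- **The protocol's 92% PPV belongs on this map.** It is for the bleeding algorithm, which is not in the primary composite.

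**Conclusion.** The point holds as an unreconciled rule in a sensitivity analysis and should be corrected. As written, the procedure can erase deaths that the same section takes as certain, and it yields a PPV axis on which the cited MI and stroke values have no place.

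In the illustration, 74 to 130 of the 185 events removed at PPV 0.86 would be deaths. The boundary lies at about 0.61, instead of 0.38, 0.20 or nowhere for death shares of 30%, 40% and 50%. These figures rest on an assumed death share, equal component hazard ratios, NPV 1 and all participants being at risk. It should not be concluded that the boundary is always misplaced. If dose has no effect on death, the deaths-fixed boundary is 0.62 to 0.65 over death shares of 20-70%, almost the same number as under the literal rule. Nor does any conclusion change at PPV 0.86: z is 2.57 or 2.76, both above 1.96. The primary test, its estimate and its alpha are unaffected.

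**What to change.** In SAP Section 7.10:

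- Define PPV and NPV on code-identified MI and stroke hospitalizations only.
- State that deaths are never reclassified. When a hospitalization is removed and the participant later died, the death becomes the primary event at its own date.
- Draw added events from a model for nonfatal MI or stroke, not from the composite Weibull model.
- Mark the protocol's MI and stroke PPVs on the heat map.

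If the intention is in fact to relax the error-free-death assumption, say so and label the axis as composite PPV. The 0 to 1 grid and Scenario 1 can stay.

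The cost is a few lines of SAP text, a filter in the program and a refitted Weibull model. No new data are needed.
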